10.2 Visit Window and the Derived Analysis Visit

The variable analysis visit will be derived to facilitate a by-visit analysis (including summary) and reporting. For efficacy parameters (eg, PANSS and CGI-S) and the 3 EPS parameters (ie, SAS, AIMS, and BARS), the analysis visit will be derived per Table 10.2-1 below. For all other parameters, the protocol-specified scheduled visit as recorded on the eSource *per se* will be simply taken as the analysis visit, and observations or assessments collected at any unscheduled visits will be programmatically mapped to an analysis visit per Table 10.2-1 below.

Protocol Amendment 5 (04 Aug 2021) updated the definition of a month duration for the purpose of scheduling monthly trial visits. The protocol month duration was changed from 4 weeks to 31 days (± 3 days). However, for analysis purposes, the same windowing will apply to all subjects, regardless of whether the assessment occurred before or after the amendment.

- 1) Observations will be mapped to an analysis visit for the 24-month open-label period based on the visit windows shown in Table 10.2-1.

Table 10.2-1 Visit Window for the 24-month Open-label Treatment Period

Analysis Visit	Trial Day	
	Allowed in Protocol	Window Specified in SAP
Day 1	1	1
Week 1	7 \pm 3	2 to 10
Week 2	14 \pm 3	11 to 20
Week 4	28 \pm 3	21 to 44
Month 2	62 \pm 3	45 to 76
Month 3	93 \pm 3	77 to 104
Month 4	124 \pm 3	105 to 160
Month 6	186 \pm 3	161 to 216
Month 8	248 \pm 3	217 to 272
Month 10	310 \pm 3	273 to 328
Month 12	372 \pm 3	329 to 412
Month 15	465 \pm 3	413 to 496
Month 18	558 \pm 3	497 to 580
Month 21	651 \pm 3	581 to 664
Month 24	744 \pm 3	665 to 790

Note: If the observation occurs 7 days after the last dose date, then Table 10.2-1 should not be used.

- 2) A subset of de novo subjects will undergo a 1- to 4-week conversion period to cross-titrate to brexpiprazole monotherapy from other antipsychotic medications. Observations in the conversion period will be mapped to an analysis visit of the conversion period based on the first dose date for the conversion period as shown in Table 10.2-2.

Table 10.2-2 Visit Window for the Conversion Period		
Analysis Visit	Allowed in Protocol	Specified in SAP
Day 1 (Conversion Period)	Day 1 in the conversion period	Same as that in protocol
Week 1 (Conversion Period)	Day 4 to 10 in the conversion period	Day 2 to 10 in the conversion period
Week 2 (Conversion Period)	Day 11 to 17 in the conversion period	Same as that in protocol
Week 3 (Conversion Period)	Day 18 to 24 in the conversion period	Same as that in protocol
Week 4 (Conversion Period)	Day 25 to 31 in the conversion period	Same as that in protocol

Note: Day # in the conversion period = observation date in the conversion period – date of the first dose of IMP in the conversion period + 1.

The above algorithm ensures that all observations that are obtained at unscheduled visits will be mapped to an analysis visit. In case that multiple observations of the same parameter on the same subject are mapped to the same analysis visit, only the last observation (in the visit window) will be used for the by-visit analyses, but all observations will be included for the data listing.

10.3 Baseline Value

If a parameter (such as AE, C-SSRS, vitals, etc) is assessed during both the conversion period and the subsequent open-label treatment period for the de novo subjects that were enrolled into both of the periods, there will be 2 baseline values: one pertinent to the conversion period and the other pertinent to the open-label treatment period.

Refer to [Section 7.1](#) for details.

10.4 Trial Completer

A trial completer is defined as those subjects in the efficacy sample who completed the scheduled assessment at the end-of-trial visit (ie, the Month 24 visit) in the 24-month open-label treatment period.

10.5 Data Imputation for the Last Assessment Visit

A landmark time point for the trial is the end-of-trial visit (the Month 24 visit) in the open-label treatment period of the trial. For some reason, a subject may be discontinued early from treatment before the end-of-trial visit. Such a subject will be invited to an ET visit where the assessments originally scheduled for the Month 24 visit will be collected.

It is anticipated that there will be many ongoing subjects at the time of the interim analysis database lock. For purposes of the interim data reporting, the LOCF rule will be applied to all subjects (including all ongoing subjects) in deriving the last visit's value for the subjects. If this trial is completed to the extent that the last enrolled subject has had an

opportunity to complete 24 months' open-label treatment, then the value at the 24-month visit or at the ET visit will be taken as the value for the last visit.

In deriving the last visit data, the LOCF rule will be applied to the following parameters: PANSS (including Total Score, Positive subscale score, Negative subscale score), CGI, SAS, AIMS, BARS, body weight, waist circumference, height, BMI, vital signs, ECG, clinical laboratory tests, CGAS, NY-AACENT, UKU Side Effects Rating Scale, Tanner Staging, and pregnancy tests. The LOCF rule will also be applicable to the individual PANSS items in deriving the last visit data. Note that only the postbaseline data can be carried forward in deriving the last visit data.

In general, the by-visit analysis (eg, summary) of a variable will also include the analysis for the derived last visit.

10.6 Descriptive Statistics for Continuous and Categorical Variables

For continuous variables, descriptive statistics include N (ie, number of subjects with non-missing value), mean, SD, median (Med), quartile, minimum (Min), and maximum (Max). For categorical (eg, nominal or dichotomous) variables, descriptive statistics refer to frequency distribution (eg, count and percentage).

In general, ordinal variables with fewer categories (say, ≤ 4) will be handled as categorical variables, whereas ordinal variables of ≥ 5 categories (such as assessment scores on many of the scales used in this trial) will be treated as continuous.

Unless specified otherwise, the denominator used for calculating percentage will be the number of unique subjects (or say, the number of subjects "at risk") in the analysis sample (or its subgroup of interest). And whenever applicable, a row of "Missing/Unknown" will be presented along with rows of recorded outcomes for the tabulation of the categorical variables.

10.7 Display of Statistical Output Tables and Listings

The data analysis (including summary) for the open-label treatment period will be performed on the analysis sample in aggregate as well as separately on 4 subgroups defined by prior treatment status as follows: (1) rollover subjects from Trial 331-10-234 who received the treatment with brexpiprazole 2 to 4 mg/day; (2) rollover subjects from Trial 331-10-234 who received the treatment with aripiprazole 10 to 20 mg/day; (3) rollover subjects from Trial 331-10-234 who received the treatment with placebo; and (4) de novo subjects. Thus, a statistical output table for the open-label treatment period will generally display the following 5 columns: (1) prior brexpiprazole, (2) prior aripiprazole, (3) prior placebo, (4) de novo, and (5) all.

However, in the situation where prior treatment cannot be unblinded (eg, for the interim data reporting before Trial 331-10-234 unblinding), statistical output tables will display the following 3 columns: (1) rollover, (2) de novo, and (3) all, where the “rollover” column pools together all 3 treatment groups from the parent Trial 331-10-234. It is anticipated that, at the time of data lock for the first interim data reporting, the parent trial will remain blinded.

In the situation where the number of de novo subjects participating in the cross-titration conversion period is 5 or fewer, statistical output tables will not be provided for the conversion period, but all the assessments, observations, or events collected in the conversion period will be included for data listings.

In general, data listings will not be presented separately for the open-label treatment period and the conversion period. Wherever appropriate, the listings should present a flagging variable (column) that indicates whether the listed observation is from the conversion period or not.

Wherever feasible, data listings should be sorted by trial period, prior treatment status, subject ID, date of assessment, visit, etc. And in general, the listing should present the sorting variables, baseline demographics, and all the variables of interest.

All statistical analysis and reporting will be generated using SAS® version 9.3 or higher.

10.8 Other Conventions

Percentage change from baseline is calculated as the change from baseline divided by the baseline value, then multiplied by 100. If the baseline value is zero, the percentage change will be undefined. If the baseline value is missing, the percentage change from baseline will be missing.

The International System of Units (Système international d'unités or SI) is the current international standard metric system. The SI units will be used for the reporting in all tables/figures/listings for this trial.

11 References

- ¹ Otsuka Pharmaceutical Development & Commercialization, Inc. A long-term, multicenter, open-label trial to evaluate the safety and tolerability of flexible-dose brexpiprazole as maintenance treatment in adolescents (13-17 years old) with schizophrenia. Otsuka Protocol 331-10-236, issued 04 May 2017, amended 01 Dec 2017, 13 Sep 2018, 03 Jun 2019, 16 Jun 2020, and 04 Aug 2021.
- ² Otsuka Pharmaceutical Development & Commercialization, Inc. Multicenter, randomized, double-blind, placebo- and active-controlled trial to evaluate the efficacy of brexpiprazole monotherapy for the treatment in adolescents (13-17 years old) with schizophrenia. Otsuka Protocol 331-10-234, issued 10 Mar 2017, amended 24 Aug 2018, 31 May 2019, 16 Jun 2020, and 05 Jul 2022.

Appendix 1**Criteria for Metabolic Change****Incidence of Treatment-Emergent Significant Change in Lipids**

Parameters	Baseline	Anytime post baseline
Total Cholesterol, fasting (mg/dl)	Normal < 170	High \geq 200
	Borderline 170 - < 200	High \geq 200
	Normal/Borderline < 200	High \geq 200
	Normal < 170	Borderline/High \geq 170
LDL-cholesterol, fasting (mg/dl)	Normal < 110	High \geq 130
	Borderline 110 - < 130	High \geq 130
	Normal/borderline < 130	High \geq 130
	Normal < 110	Borderline/High \geq 110
HDL-cholesterol, fasting (mg/dl)	Normal > 45	Low < 40
	Borderline 45 - \geq 40	Low < 40
	Normal/Borderline \geq 40	Low < 40
	Normal > 45	Borderline/Low \leq 45
Triglycerides, fasting (mg/dl)	Normal < 90	High \geq 130
	Borderline 90 - < 130	High \geq 130
	Normal/borderline < 130	High \geq 130
	Normal < 90	Borderline/High \geq 90

Incidence of Treatment-Emergent Significant Change in Glucose

Parameters	Baseline	Anytime post baseline
Glucose fasting, serum (mg/dl)	Normal < 100	High \geq 126
	Impaired 100 - < 126	High \geq 126
	Normal/impaired < 126	High \geq 126
	Any Value	increased \geq 10

Appendix 2 Additional Criteria for Blood Pressure

Parameter	Criteria	Change Relative to Baseline
Systolic Blood Pressure (Any position)	< 90 mmHg or > 120 mmHg	Increase or decrease of ≥ 15 mmHg
Diastolic Blood Pressure (Any position)	< 60 mmHg or > 85 mmHg	Increase or decrease of ≥ 15 mmHg

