**Appendix 1****Criteria for Identifying Vital Signs of Potential Clinical Relevance**

| Variable                              | Criterion Value a  | Change Relative to Baseline a           |
|---------------------------------------|---|--|
| Heart Rate b               | > 120 bpm
< 50 bpm   | ≥ 15 bpm increase
≥ 15 bpm decrease             |
| Systolic Blood Pressure b  | > 180 mmHg
< 90 mmHg   | ≥ 20 mmHg increase
≥ 20 mmHg decrease           |
| Diastolic Blood Pressure b | > 105 mmHg
< 50 mmHg   | ≥ 15 mmHg increase
≥ 15 mmHg decrease           |
| Orthostatic Hypotension               | ≥ 20 mmHg decrease in systolic blood pressure and a ≥ 25 bpm increase in heart rate from supine to sitting/standing | Not Applicable
(baseline status not considered) |
| Weight                                | -   | ≥ 7% increase
≥ 7% decrease                     |

aIn order to be identified as potentially clinically relevant, an on-treatment value must meet the “Criterion Value” and also represent a change from the subject’s baseline value of at least the magnitude shown in the “Change Relative to Baseline” column.

bAs defined in “Supplementary Suggestions for Preparing an Integrated Summary of Safety Information in an Original NDA Submission and for Organizing Information in Periodic Safety Updates,” FDA Division of Neuropharmacological Drug Products draft (2/27/87).

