8.2.4 Vital Signs Data

8.2.4.1 Data Collected in the Open-label Treatment Period

Vital signs will be assessed at all scheduled visits across the 24-month open-label treatment period. Vital signs parameters include body temperature, systolic blood pressure (SBP), diastolic blood pressure (DBP), and pulse (ie, heart rate), of which SBP and DBP and pulse will be measured in the supine, sitting, and standing positions.

Measurements obtained in different positions will be treated as different parameters for purposes of the data summary. Thus, there are a total of 10 vital signs parameters for this trial.

For the 24-month open-label treatment period, assessment values and change from baseline values in each vital signs parameter will be summarized on the OC data by visit and additionally on the LOCF data for the last assessment visit.

Additionally, change from baseline to the lowest value postbaseline and to the highest value postbaseline in each parameter will be respectively summarized on the OC data for the overall 24-month open-label treatment period.

Potentially clinically significant vital signs abnormalities during the 24-month open-label treatment period will be identified, and the incident (ie, number and percentage of subjects who had such an abnormality) in each parameter will be tabulated by visit and at the subject level for the overall open-label treatment period. All potentially clinically significant vital signs abnormalities will be listed by prior treatment group, subject ID, visit, and vital signs parameter, along with baseline value, age, sex, body weight, and

dose at onset of the event of abnormality. Refer to Appendix 1 of the protocol for the criteria for identifying vital signs of potential clinical relevance. In addition to the protocol criteria, blood pressure criteria provided in Appendix 2 will be applied.

If a subject has repeat measures in a parameter at a visit, only the last repeat for the visit will be used for the analysis or summary. But all data from the same visit, including repeats and unscheduled visits, will be used for the data listing.

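### SAP Appendix 2 does not tie the direction of blood pressure change to the limit crossed, so a fall from a high systolic value can be flagged as an abnormality

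*SAP*

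**What the plan says.** SAP section 8.2.4.1 identifies potentially clinically significant vital signs abnormalities in the open-label period, tabulates their incidence by visit and over the whole period, and lists every one with baseline value and dose at onset. The criteria are those of Protocol Appendix 1, plus a second set: "In addition to the protocol criteria, blood pressure criteria provided in Appendix 2 will be applied". Section 8.2.4.2 carries the same approach into the conversion period.

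SAP Appendix 2 has one row per parameter, applying in any position. The systolic limits are "< 90 mmHg or > 120 mmHg", the diastolic limits are "< 60 mmHg or > 85 mmHg", and the change column for each is "Increase or decrease of ≥ 15 mmHg".

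Protocol Appendix 1 is laid out differently. Its systolic limits (above 180, then below 90 mmHg) stand beside "≥ 20 mmHg increase ≥ 20 mmHg decrease", and its diastolic limits (above 105, then below 50 mmHg) beside "≥ 15 mmHg increase ≥ 15 mmHg decrease". Line by line, the upper limit goes with the increase and the lower limit with the decrease. A footnote says that a value must meet the limit and must also be a change from the subject's "baseline value of at least the magnitude shown in the" change column. SAP Appendix 2 has neither the line-by-line pairing nor the footnote.

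**The concern.** A limit-plus-change criterion is meant to pick out readings that have moved into an abnormal range. When either direction of change satisfies the second condition, the rule also picks out readings that are still beyond a limit but have moved back towards normal.

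Protocol section 3.5.2.1 makes the incidence of clinically significant vital signs abnormalities a secondary safety endpoint. Literal coding adds improvements to that count, mostly among subjects who start with high systolic pressure. It also puts them in the by-subject listing with a dose at onset, where a safety reader would take them for events arising on treatment. Two programmers, one following the text and one following the protocol's pairing, would produce different counts.

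**Working it through.** The plan gives no figure to reproduce. The check is one of logic, followed by an illustration of size.

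**1. The two rules.** Let b be baseline and x the on-treatment reading, with limits lo/hi of 90/120 (systolic) and 60/85 (diastolic) from SAP Appendix 2.

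- Literal rule: (x < lo or x > hi) and |x − b| ≥ 15.
- Paired rule: (x < lo and b − x ≥ 15) or (x > hi and x − b ≥ 15).

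The literal rule takes its *and* from the Protocol Appendix 1 footnote. If the two columns were read as alternatives, the same wrong-direction readings would be flagged, along with many others. Reading the cells as *respectively* does not help: the order is low then high against increase then decrease, which would pair low with increase.

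**2. Worked systolic readings**

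| b → x (mmHg) | Change | Literal | Paired |
|---|---|---|---|
| 145 → 125 | −20 | flagged | not flagged |
| 140 → 122 | −18 | flagged | not flagged |
| 136 → 121 | −15 | flagged | not flagged |
| 110 → 126 | +16 | flagged | flagged |

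Protocol Appendix 1 flags none of these four. Every reading flagged by the paired rule is also flagged by the literal rule, so the error can only add flags.

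**3. Who can be affected (whole mmHg)**

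- Systolic high after a fall: x ≥ 121 and b ≥ x + 15, so b ≥ 136.
- Systolic low after a rise: x ≤ 89 and b ≤ x − 15, so b ≤ 74.
- Diastolic high after a fall: x ≥ 86, so b ≥ 101.
- Diastolic low after a rise: x ≤ 59, so b ≤ 44.

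Rollover exclusion criterion 8 and de novo criterion 13 exclude uncontrolled hypertension, defined by diastolic pressure above 95 mmHg, and give no numeric systolic ceiling. The third case should therefore hardly arise, and the second and fourth need very low baselines. The first can arise.

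**4. Why regression to the mean feeds it.** Assume mean 115, SD 11, correlation 0.5 and no drug effect. A subject with b = 145 has an expected follow-up reading of 115 + 0.5 × (145 − 115) = 130, with conditional SD 11 × √(1 − 0.25) = 9.53. Wrong-direction flags are readings from 121 to 130. Their probability is Φ((130.5 − 130)/9.53) − Φ((120.5 − 130)/9.53) = 0.52 − 0.16 = 0.36 at one reading.

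**5. Size per systolic reading.** Bivariate normal simulation of baseline and follow-up with equal means and SDs; all distribution inputs are assumptions:

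| Mean | SD | Correlation | Literal | Paired | Wrong-direction share of flags |
|---|---|---|---|---|---|
| 112 | 11 | 0.4 | 7.9% | 7.6% | 4% |
| 115 | 11 | 0.5 | 7.1% | 6.6% | 7% |
| 117 | 12 | 0.5 | 9.7% | 8.6% | 11% |
| 122 | 12 | 0.6 | 9.1% | 7.2% | 21% |

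Rounding to whole mmHg changes the last row to 9.7% against 7.7%, with the share still 21%. A slightly different grid (mean 110 to 120, SD 10 to 12, correlation 0.5 to 0.7) gives shares of 2% to 19%, or 0.06% to 1.8% of subjects per visit and position.

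For diastolic pressure (mean 70 to 75, SD 8 to 10, correlation 0.4 to 0.6, baseline capped at 95) the share is under 3%. At an assumed mean of 65 it reaches 7%, which is at most 0.4% of readings.

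**The case against.** The strongest reply is that Appendix 2 is a condensed supplement to Protocol Appendix 1, and a programmer extending that table would probably carry its pairing over, just as the literal reading above borrows the protocol's both-columns rule. On that view the text is loose rather than wrong, and the harm arises only if it is coded word for word. This does not remove the point. The change column is not silent on direction: it admits both. A programmer who pairs the directions departs from the written SAP.

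Other limits are fair and stand:

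- The protocol's own criteria are direction-paired and still apply. The SAP does not say, however, whether flags from the two sets are pooled or shown apart.
- In practice only one of the four cells matters, systolic high after a fall.
- The listing carries the baseline value, and section 8.2.4.1 also summarises change to the lowest and highest values, so direction can be recovered, though not from the incidence table.
- The 21% is the top of an assumed range; mid-range values give about 7% to 11%.
- The figures are per reading. A subject who attends all 14 scheduled clinic visits after Day 1, measured in three positions, gives 14 × 3 = 42 systolic readings, and incidence over the whole period was not simulated.
- No inferential analysis is planned.

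**Conclusion.** The concern holds. As written, SAP Appendix 2 counts a systolic reading above 120 mmHg that has fallen by 15 mmHg or more as an abnormality, and no other part of the SAP corrects this. The direction of the error is certain: it can only inflate the count. Its size depends on the trial's systolic distribution, which the documents do not give. Under the assumptions shown, wrong-direction flags are 4% to 21% of systolic flags per reading, an excess of 0.3 to 1.9 percentage points in the tabulated scenarios. The diastolic effect is small. The consequence is confined to descriptive incidence tables and listings for a secondary safety endpoint, so this is a minor correction.

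**What to change.** Rewrite SAP Appendix 2 as four rows, keeping every threshold:

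- systolic above 120 mmHg with an increase of at least 15 mmHg;
- systolic below 90 mmHg with a decrease of at least 15 mmHg;
- diastolic above 85 mmHg with an increase of at least 15 mmHg;
- diastolic below 60 mmHg with a decrease of at least 15 mmHg.

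Add one sentence saying that the limit and the change must both be met. Tabulate high and low flags on separate lines. This goes a little beyond the defect itself, but it follows naturally from four rows and makes the direction visible in the incidence table. It would also help to say whether Appendix 2 flags are shown apart from those under Protocol Appendix 1.

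The cost is wording in a SAP appendix and a small change to the flagging code, with no new data and no protocol amendment. It should be done before the tables for the next database lock are programmed. If interim tables have already used the literal rule, the affected blood pressure rows need to be rerun.
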